## 1.2 Study design

This is a Phase IV, multicenter, randomized, double-blind, placebo-controlled, parallel-group study evaluating the effect of Acclidinium Bromide (a long-acting muscarinic antagonist delivered by the Pressair® dry powder inhalation [DPI] device) compared with placebo on long-term CV safety and COPD exacerbations in outpatients at least 40 years of age who have been diagnosed with moderate to very severe COPD (postbronchodilator % predicted forced expiratory volume in 1 second [FEV1] < 80% and FEV1/forced vital capacity [FVC] ratio < 70%) and a history of CV or cerebrovascular disease and/or significant CV risk factors.

Note: in this document

1. The term “double-blind treatment period” applies to the following 2 scenarios:
  - When used in “maximum of 36-months double-blind treatment period”
  - When used for patients who completed 36-months treatment (completer)
2. The term “during the treatment period” refers to on-treatment period.
3. The term “during the whole study period” refers to both on-treatment and off-treatment (post-treatment follow-up) periods.

The study consists of two-week washout/run-in period (for patients on a long-acting muscarinic antagonist [LAMA]) followed by a maximum of 36-month double-blind treatment period.

Signed informed consent form (ICF) from the patient or the patient’s legally authorized representative will be obtained before any study-related procedures are begun. All patients will be assigned a patient identification (PID) number via the interactive web response system (IWRS). Patients meeting the entry criteria for this study will be randomized (1:1) to acclidinium bromide 400 µg (abbreviated as acclidinium hereafter) twice a day (BID) or placebo BID. This study will conclude when 122 patients have experienced an adjudicated MACE.

Patients who prematurely discontinue investigational product (IP) will participate in a post-treatment follow-up period. The follow-up period will include on-site visits and telephone visits to collect MACE, COPD exacerbations, concomitant medications, and SAEs for the remainder of the study duration.

An independent Data Safety Monitoring Board (DSMB) will be established for this study. The DSMB will periodically monitor and review relevant clinical safety data, including adjudicated MACE.

Patients will be assessed according to the Schedule of Evaluations (See Section 2 of the clinical study protocol [CSP]).

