#### 3.1.7.2 Duration of event

For the production of summary statistics, the duration (in days) of event per patient per year during a given period is calculated as the sum of duration of all available events in that period divided by the sum of all patients follow-up time in that period, i.e.,  $\frac{\sum_{i=1}^n p_i}{\sum_{i=1}^n t_i}$ , where  $p_i$  is the duration (in days) of all events in patient  $i$ . The duration of each event is calculated as (*end date – onset date + 1*).

See Section 3.1.7.1 for calculation of the follow-up time in patient  $i$ ,  $t_i$ .

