### **3.4 Additional efficacy variables**

#### **3.4.1 COPD exacerbation variables**

The following COPD exacerbation variables use data collected during the whole study period. Maximum follow-up time for a patient is approximately 36 months.

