##### **3.4.1.3 Duration of moderate or severe COPD exacerbations per patient per year**

For the production of summary statistics, the duration (in days) of moderate or severe COPD exacerbation per patient per year is calculated by applying the following in the general formula defined in Section 3.1.7.2.

- Event is moderate or severe COPD exacerbation
- Period refers to the whole study period

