##### **3.4.1.4 Duration of mild, moderate, or severe COPD exacerbations per patient per year**

For the production of summary statistics, the duration (in days) of mild, moderate, or severe COPD exacerbation per patient per year is calculated by applying the following in the general formula defined in Section 3.1.7.2.

- Event is mild, moderate, or severe COPD exacerbation
- Period refers to the whole study period

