In addition, the Kaplan-Meier survival curves will be displayed for each treatment group along with p-value for differences (aclidinium over placebo) based on the Log-Rank test stratified by baseline COPD severity and smoking status.

The durations of COPD exacerbation (any, and moderate or severe; in days) will be summarized descriptively for only the patients who had exacerbations during the treatment period.

Number of days hospitalized due to COPD exacerbations will be summarized for only the patients who had exacerbations during the treatment period. The descriptive statistics of number of days hospitalization due to COPD exacerbations will be summarized by unit type (any, hospitalization unit, intensive care unit, emergency room).

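### Exacerbation duration is defined as days per patient-year over all patients, but the only planned summary covers patients who had an exacerbation, in an unstated unit

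*SAP*

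**What the plan says.** Section 3.1.7.2 gives the formula intended for summary statistics on duration. The total of event days is "divided by the sum of all patients follow-up time in that period", with both sums running over all n patients.

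Sections 3.4.1.3 and 3.4.1.4 apply it to two event sets. For moderate or severe events, "the duration (in days) of moderate or severe COPD exacerbation per patient per year is calculated by applying the following in the general formula"; for events of any severity, "the duration (in days) of mild, moderate, or severe COPD exacerbation per patient per year is calculated by applying the following in the general formula". Both name the whole study period. Section 3.4.1 repeats this ("The following COPD exacerbation variables use data collected during the whole study period"), and Section 1.2 explains that the term "refers to both on-treatment and off-treatment (post-treatment follow-up) periods".

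In Section 4.2.4.3, under the analyses for COPD exacerbations, durations in days (any, and moderate or severe) "will be summarized descriptively for only the patients who had exacerbations during the treatment period". No model or test is planned. Days in hospital get the same restriction in the next paragraph, but Section 3.4.1.9 defines them as a plain sum of days, with no patient-year denominator. Section 4.2.4.3 opens by saying that, unless otherwise specified, its variables use whole-study data under the on-treatment analysis. Section 4.2.4 bases all efficacy analyses on the FAS.

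**The concern.** The definition and the analysis describe different quantities. The first divides by everyone's follow-up, so a patient with no exacerbation contributes zero days and full follow-up time. The second drops that patient. Two programmers could produce different tables from this text, and the variable named in Sections 3.4.1.3 and 3.4.1.4 could go unreported.

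The restricted table also has a design weakness. Having an exacerbation happens after randomization and is what the drug is meant to reduce. Patients whose exacerbations were prevented leave the table, and more of them leave the active arm. The groups left are no longer the randomized ones, and a reduction in the number of events is pulled towards no difference.

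**Working it through.** **Inputs.** From Section 1.3.2: placebo rate 0.8 per patient-year, rate ratio 0.86 (so 0.8 × 0.86 = 0.688 on aclidinium), k = 0.67, 30% treatment discontinuation in year 1, 4,000 patients. From Section 1.2: 1:1 allocation, so 2,000 per arm. From Section 1.3.1: 40% treatment discontinuation at year 2 and 6,500 patient-years, so 6,500/4,000 = 1.625 years per patient.

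**Assumptions not in the SAP.** Mean days per event are equal in both arms, so they cancel from every ratio. The first-year rate, rate ratio and k hold over the whole follow-up.

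**Step 1: reproduce the SAP's power.** For a negative binomial Wald test on the log rate ratio, Var = [(1/(0.8t) + k) + (1/(0.688t) + k)]/2,000. With mean exposure t = 0.85 (30% leaving evenly over the year), Var = (1.471 + 0.67 + 1.710 + 0.67)/2,000 = 0.00226 and SE = 0.0475. Then z = 0.1508/0.0475 − 1.96 = 1.21, and power is 88.7%. Exponential discontinuation (t = 0.841) gives 88.5%. Both agree with the stated figure of about 89%, so the inputs are read as the SAP intended.

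**Step 2: the defined quantity.** With equal days per event, the ratio of days per patient-year over all patients equals the rate ratio, 0.86.

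**Step 3: total days per patient, exacerbators only.** With mean count μ = rate × t, P(Y ≥ 1) = 1 − (1 + kμ)^(−1/k) and E[Y | Y ≥ 1] = μ/P(Y ≥ 1). At one year:

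- Placebo: μ = 0.8, P = 0.473, mean 0.8/0.473 = 1.691 events.
- Aclidinium: μ = 0.688, P = 0.432, mean 0.688/0.432 = 1.592 events.
- Ratio 1.592/1.691 = 0.941. More than half of each arm (52.7% and 56.8%) is left out.

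The share of the log effect that is hidden is 1 − ln(ratio)/ln(0.86). Where discontinuation is exponential, the mean count and P(Y ≥ 1) are averaged over the exposure distribution, with hazard −ln(0.7) per year for the first-year row and −ln(0.6)/2 for the three-year row.

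| Follow-up | P(Y ≥ 1), placebo / aclidinium | Events per exacerbator, placebo / aclidinium | Ratio | Log effect hidden |
|---|---|---|---|---|
| 0.85 years for all | 0.429 / 0.390 | 1.585 / 1.502 | 0.947 | 64% |
| First year, 30% discontinuation, exponential | 0.410 / 0.374 | 1.639 / 1.549 | 0.945 | 62% |
| 1 year, full | 0.473 / 0.432 | 1.691 / 1.592 | 0.941 | 60% |
| 1.625 years for all | 0.607 / 0.566 | 2.140 / 1.976 | 0.923 | 47% |
| Up to 3 years, 40% discontinued at year 2, exponential | 0.611 / 0.577 | 2.743 / 2.500 | 0.912 | 39% |
| 3 years, full | 0.761 / 0.726 | 3.154 / 2.842 | 0.901 | 31% |

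The hidden share falls below half once follow-up passes about 1.45 years (1.2 to 1.6 years for an assumed k from 1.5 to 0.3).

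**Step 4: days per episode.** If that is the unit, the ratio is 1.00 by construction under equal days per event, and none of the frequency effect shows.

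**Step 5: any-severity events.** The SAP gives no rate for these. It cannot be lower than the moderate-or-severe rate, and a higher rate weakens the dilution: at an assumed 1.2 per year, the one-year ratio is 0.926 instead of 0.941.

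**The case against.** The strongest reply is that the two sections describe different outputs. Section 3 would give the all-patient rate of days. Section 4.2.4.3 speaks only of durations in days, which can mean episode length, and that exists only in patients with an episode. The wording allows this reading. It does not close the gap, because Section 4 nowhere calls for the Section 3 quantity and the unit of the restricted table is still unstated.

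The second reply is about weight, and it stands. The table is descriptive, has no test or model and lies outside the testing sequence. Frequency is analysed in the FAS by negative binomial rates, logistic regression and time-to-event models. No inference rests on duration.

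The third concerns the period. Section 1.2 equates the treatment period with the on-treatment period, and the opening of Section 4.2.4.3 prescribes an on-treatment analysis, so the restriction follows that rule. What remains is a tension with Sections 1.2 and 3.4.1, where the whole study period includes time off treatment.

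A reader might infer that the restricted table hides most of any treatment effect. The documents do not support that. On total days per patient, more than half is hidden only over roughly the first year and a half, while duration is a whole-study variable with up to about 36 months of follow-up. All of the frequency effect is hidden only on the per-episode reading. An effect on episode length alone would not be hidden. A reader might also take hospital days to contradict Section 3.1.7.2, but Section 3.4.1.9 does not invoke that formula.

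**Conclusion.** The point holds as a mismatch between definition and analysis for duration, together with a summary that conditions on a post-randomization outcome. For total days per patient, the restricted table would hide about 31% to 47% of the log frequency effect at 1.6 to 3 years and about 60% to 64% over the first year. On the per-episode reading it would hide all of it. These figures rest on the SAP's moderate-or-severe planning rates, a negative binomial count, equal days per event and a constant rate over follow-up. For hospital days only the selection problem applies. The importance is low, because the variable is additional, descriptive and untested, and frequency is estimated elsewhere in all FAS patients.

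**What to change.** - In Section 4.2.4.3, state that days of exacerbation per patient-year, as Section 3.1.7.2 defines them, will be reported by arm in all FAS patients, for any and for moderate or severe events. Patients without an event contribute zero days and their full follow-up time.
- Keep the exacerbator-only table as a supplement. Label it as a comparison of non-randomized subsets and state its unit, per episode or per patient.
- Align the period wording across Sections 1.2, 3.4.1 and 4.2.4.3, so that event days and follow-up time come from the same period.
- For hospital days, add a summary in all FAS patients with zero for those not hospitalized, keeping the Section 3.4.1.9 definition.

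The cost is SAP wording and one extra table. No new data are needed.

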#### **Analyses for spirometry variable**

Change from baseline in morning pre-dose (trough) FEV1 by visit (on-treatment analysis) will be compared between aclidinium group and placebo using a MMRM model on patients with a baseline pre-dose/pre-bronchodilator FEV1 and at least one post-randomization pre-dose FEV1 in the FAS Population. The dependent variable will be the change from baseline in pre-dose FEV1 at postbaseline protocol-specified visits (up to Visit 12 or EOT visit). Treatment group will be fitted as the explanatory variable, and pre and post-bronchodilator (albuterol/salbutamol) FEV1 at screening visit (Visit 1A), and baseline FEV1 as covariates, and smoking status, baseline ICS use, visit, and treatment group-by-visit interaction as fixed effect factors. Visit will be fitted as a categorical variable, and the variance-covariance matrix will be assumed to be unstructured. Kenward Roger approximation will be used to estimate denominator degrees of freedom. If the procedure does not converge then a compound symmetric variance-covariance matrix will be used instead. The model is as follows:

*Change in FEV1 = treatment group + pre-bronchodilator FEV1 at Screening + post-bronchodilator FEV1 at Screening + baseline FEV1 + smoking status + Baseline ICS use + visit + treatment\*visit*

Each treatment effect and treatment difference between aclidinium and placebo at each visit will be estimated by their least squares (LS) means and the differences in LS means on the treatment-by-visit interaction, along with their standard errors (SEs), and 95% CIs and the p-value corresponding to the between-treatment-group difference. In addition, the overall treatment effect and treatment difference over the treatment period will be estimated by the LS means and the difference in LS means on the treatment factor, along with the SEs, and 95% CIs and the p-value corresponding to the between treatment group difference.

A longitudinal plot will be used to display the change from baseline in FEV1 at each visit by treatment group.

In addition, change from baseline in morning pre-dose (trough) FEV1 by visit (on-treatment analysis) will be analyzed for the following 2 subgroups:

- LABA users (with and without ICS)
- LABA/ICS users

That is, data for each subgroup will be extracted first, then do analysis on each set of data using the same approach as the corresponding primary analysis.

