## **1.3 Number of subjects**

### **1.3.1 Power for the primary safety endpoint: time to first MACE event**

For this study, a total of 122 patients with MACE will be needed to have 90% power, at 5% significance level, to rule out a hazard ratio of 1.8 in time to first MACE in acclidinium bromide treated patients relative to placebo, assuming the hazard rate is 1.0 under the alternative hypothesis. The justification for the hazard ratio of margin of 1.8 is provided in Appendix IV of the CSP.

This ASCENT COPD study will be recruiting patients with a FEV1 below 80% and a planned maximum of 36 months double-blind treatment period. The assumption of 1.9 MACE per 100 patient years would be reasonable for this study (See Section 9.7.9.1 of the CSP for details). To obtain 122 MACE in this study with 1.9 MACE per 100 patient years of treatment, a total of 6,500 patient years of treatment (aclidinium bromide and placebo) would be needed. Assuming a treatment discontinuation rate of 40% and a study discontinuation rate of 20% at year 2, and following an exponential distributions for time to events and time to discontinuations, a sample size of 4000 is needed to ensure 90% power to observe 122 events applying the on-study analysis, and an 80% power to observe 91 events applying the on-treatment analysis.

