### **1.3.2 Power for the primary efficacy endpoint: rate of moderate or severe exacerbations per patient per year during the first year of treatment**

The sample size of 4,000 patients after 1 year of treatment will have ~89% power to detect a reduction in the rate of moderate or severe COPD exacerbations per patient per year during the first year of treatment of 14% (rate ratio of 0.86 in acclidinium bromide relative to placebo) at 0.05 significance level. The 89% power was calculated assuming a treatment discontinuation rate of 30% during the first year, a placebo rate of 0.8 exacerbation per patient per year (reduced from 1 to 0.8 as not all patients will have a history of exacerbation prior to randomization), and an overdispersion factor  $k$  of 0.67 (Keene et al, 2007).

See Section 9.7.9 of the CSP for detailed information on determination of sample size and power calculation.

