#### **4.2.4 Efficacy analyses**

All efficacy analyses will be based on the FAS Population. All statistical tests will be two-sided hypothesis tests performed at the 0.05 significance level for main effects. All CIs will be two-sided 95% CIs. No multiplicity adjustment will be made to CIs as they will be interpreted descriptively and used as a measure of precision. All p-values will be unadjusted.

To control for multiplicity, the primary and secondary efficacy variables will be tested sequentially, i.e., the secondary efficacy endpoint will be tested only when both primary and secondary analyses on the primary efficacy endpoint achieved statistical significance, and the secondary analysis on the primary efficacy endpoint will be tested only when the primary analyses on the primary efficacy endpoint achieved statistical significance. Otherwise, nominal p-values will be provided and should be interpreted descriptively.

Analyses on COPD exacerbations will be based on definitions as described in Section 3.1.6.

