### **4.2.6 Health economics and outcomes research analyses**

#### **4.2.6.1 COPD assessment tests (CAT) by visit**

Descriptive statistics will be provided at baseline (actual scores) and each postbaseline visit (actual and change from baseline scores).

Change from baseline in CAT total score by visit will be compared between aclidinium group and placebo using a MMRM model on patients with a baseline CAT total score and at least

one post-randomization CAT total score in the FAS Population. The dependent variable will be the change from baseline in CAT total score at postbaseline protocol-specified visits (up to Visit 12 or EOT visit). Treatment group will be fitted as the explanatory variable, and baseline CAT total score as covariate, and baseline ICS use, smoking status, visit, and treatment group-by-visit interaction as fixed effect factors. Visit will be fitted as a categorical variable, and the variance-covariance matrix will be assumed to be unstructured. Kenward Roger approximation will be used to estimate denominator degrees of freedom. If the procedure does not converge then a compound symmetric variance-covariance matrix will be used instead. The model is as follows:

*Change in CAT total score = treatment group + baseline CAT total score + baseline ICS use + smoking status + visit + treatment\*visit*

Each treatment effect and treatment difference between aclidinium and placebo at each visit will be estimated by their LS means and the differences in LS means on the treatment-by-visit interaction, along with their SEs, and 95% CIs and the p-value corresponding to the between-treatment-group difference. In addition, the overall treatment effect and treatment difference over the treatment period will be estimated by the LS means and the difference in LS means on the treatment factor, along with the SEs, and 95% CIs and the p-value corresponding to the between treatment group difference.

A longitudinal plot will be used to display the change from baseline in CAT total score at each visit by treatment group.

Change from baseline in CAT total score by visit will be analyzed for the following 2 subgroups:

- LABA users (with and without ICS)
- LABA/ICS users

That is, data for each subgroup will be extracted first, then do analysis on each set of data using the same approach as the primary analysis.

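### The FEV1 and CAT repeated-measures models hold each baseline slope constant over all visits; if slopes drift, late-visit precision suffers, and arm means or differences can be biased under further conditions

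*SAP*

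**What the plan says.** The spirometry part of SAP section 4.2.4.3 writes out the FEV1 model. Change in FEV1 "by visit (on-treatment analysis) will be compared between aclidinium group and placebo using a MMRM model". The covariates are screening pre-bronchodilator FEV1, screening post-bronchodilator FEV1 and baseline FEV1, with "smoking status, baseline ICS use, visit, and treatment group-by-visit interaction as fixed effect factors". On covariance: "Visit will be fitted as a categorical variable, and the variance-covariance matrix will be assumed to be unstructured"; compound symmetry is the fallback if the fit does not converge.

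Section 4.2.6.1 builds the CAT model in the same way: "baseline CAT total score as covariate, and baseline ICS use, smoking status, visit, and treatment group-by-visit interaction as fixed effect factors".

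In both written-out models the only terms involving visit are visit itself and treatment by visit. Both report arm LS means and treatment differences with intervals and p-values at each visit, plus an overall difference and a plot over time. FEV1 is analysed at eight visits (section 3.4.2) and CAT at ten (section 3.6).

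On duration, section 3.4.1 says: "Maximum follow-up time for a patient is approximately 36 months". On discontinuation, section 1.3.2 plans "assuming a treatment discontinuation rate of 30% during the first year", and section 1.3.1 has "Assuming a treatment discontinuation rate of 40% and a study discontinuation rate of 20% at year 2". The post-treatment follow-up described in section 1.2 lists neither spirometry nor CAT among the data collected.

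**The concern.** The models leave visit, treatment by visit and the covariance free, but tie each baseline covariate to a single slope. For a model with one baseline covariate, such as CAT, the slope of change on baseline at visit t is cov(Y_t, Y_0)/var(Y_0) - 1. A constant slope therefore requires every visit, from the first to the last, to covary equally with baseline. The SAP gives no reason for this restriction. The same reasoning applies to the partial slopes in the FEV1 model.

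If the restriction is wrong, the common slope misfits the late visits. By then a substantial share of patients is expected to be off treatment, so the model has to predict much of what is missing. The per-visit results are what is at stake. The missing-data sensitivity analyses in section 4.2.4.1 cover the primary efficacy endpoint; the SAP plans none for either MMRM.

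**Working it through.** **No figure to reproduce.** The SAP gives no SD, effect size or power for FEV1 or CAT. The check is therefore of mechanism and order of size, under stated assumptions.

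**Algebra (first order).** Let β_t be the true slope at visit t, b the fitted common slope, and m_0 and m_1 the mean baselines, relative to the overall mean, of the placebo and aclidinium patients still observed.

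- Bias of an arm's LS mean ≈ (β_t - b) × m_arm.
- Bias of the difference ≈ (β_t - b) × (m_1 - m_0).
- SE ratio ≈ √[1 + (β_t - b)² σ_B² / σ²], with σ_B the baseline SD and σ the residual SD.

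So the interval widens with drift alone. An arm mean is biased if there is drift and dropout depends on baseline. The difference is biased only if, in addition, m_1 ≠ m_0.

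**Rough size of the widening.** Assume σ_B = 0.5 L, σ = 0.22 L and b at the middle of the drift:

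- Slope -0.05 to -0.20: β_t - b = -0.075; √(1 + 0.0375²/0.22²) = 1.014.
- Slope -0.05 to -0.35: β_t - b = -0.15; √(1 + 0.075²/0.22²) = 1.056.
- Slope -0.10 to -0.50: β_t - b = -0.20; √(1 + 0.10²/0.22²) = 1.098.

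**Simulation.** Maximum-likelihood MMRM, unstructured covariance, eight visits, one baseline covariate, monotone dropout after the first visit driven by baseline, about 59% complete at the last visit, true difference 60 mL. Each dataset was fitted with the common slope and with baseline by visit. The table shows last-visit results in mL for n = 3,600 and 100 replicates; ± is Monte Carlo error. Dropout slopes are logits per SD of baseline, placebo versus aclidinium.

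| Drift | Dropout | Bias of difference, common slope | Same, by visit | Placebo mean bias, common slope | SE ratio |
|---|---|---|---|---|---|
| -0.05 to -0.20 | equal in both arms (-0.5) | -0.7 ± 1.1 | -0.8 | -9.5 | 1.021 |
| | same slope, more on placebo | +3.6 ± 0.9 | +0.4 | -12.5 | 1.021 |
| | mildly different (-0.6 vs -0.4) | +2.8 ± 0.8 | -0.8 | -10.8 | 1.020 |
| | strongly different (-0.8 vs -0.2) | +12.3 ± 0.9 | +1.2 | -15.3 | 1.016 |
| -0.05 to -0.35 | equal in both arms | +1.6 ± 0.9 | +1.0 | -19.8 | 1.082 |
| | same slope, more on placebo | +6.1 ± 0.8 | +0.5 | -21.9 | 1.081 |
| | mildly different | +6.9 ± 1.1 | -0.5 | -21.2 | 1.081 |
| | strongly different | +21.4 ± 1.0 | -0.3 | -28.4 | 1.076 |

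The ratios are of model-based SEs. The empirical SD of the estimate was also smaller with baseline by visit in all eight rows.

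**Single large fits (n = 60,000; Monte Carlo SE 2.2 mL).**

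- Drift -0.10 to -0.50 gave SE ratios of 1.125 to 1.146.
- A flat slope of -0.15 gave no bias beyond simulation error in either model and ratios of 0.987 to 1.000.
- In a stress case with dropout slopes of -1 versus 0, the common-slope bias was +17, +38 and +41 mL for the three drifts.

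**Separate large-sample simulation.** With 30,000 per arm, drifts from -0.08 to -0.20 or -0.05 to -0.25, and assumed discontinuation of 45% on placebo and 35% on aclidinium at two years, the shifts from the common slope were 2.8, 5.9, 8.9 and 9.4 mL. The variance ratios were 1.03, 1.03, 1.02 and 1.08, that is, SE ratios of about 1.015, 1.015, 1.010 and 1.04. A constant-slope control moved by -0.2 mL.

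**Scale.** Biases of 3, 9, 12 and 21 mL are 5%, 15%, 20% and 35% of the assumed 60 mL. If the exponential assumption of section 1.3.1 is carried to month 36, 0.6^1.5 = 0.46 remain on treatment, so 59% complete is the milder setting.

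**The case against.** Neither model is misstated or contradictory. Baseline as a main effect is a familiar ANCOVA-type choice, and the SAP specifies the covariance, the degrees of freedom and a fallback. Slope drift, baseline-dependent dropout and a difference in that dropout between arms are all assumed here; the SAP states none of them. The mild biases are small: 2.8 mL is about a third of the last-visit SE of about 9 mL. Only the last visit was quantified, whereas the SAP singles out no visit and also reports an overall difference. The simulated model has one baseline covariate and the SAP's FEV1 model has three. CAT was not simulated. All of this stands, and it lowers the severity. It does not show that the common slope is as good a choice, since the freer model lost at most about 1% in SE when the slope was flat.

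A reader might infer that dropout related to baseline biases the treatment difference by itself, given the 30% and 40% figures. The documents do not support that. Those figures are overall planning assumptions, not split by arm. With equal dropout in both arms the error in the arm means cancels (-0.7 ± 1.1 and +1.6 ± 0.9 mL). Nor is dropout the source of the wider intervals; that is the drift.

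A reader might also cite Appendix 1, which takes missing values to be related to treatment. That is a working assumption for imputing exacerbations, not evidence about FEV1 or CAT.

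**Conclusion.** The point holds in conditional form.

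- **Slope drift alone:** the late-visit difference is less precise than it could be, with an SE about 1-8% larger under most assumed drifts and up to about 15% under strong drift.
- **Drift plus dropout that depends on baseline:** late-visit arm means, and the plots over time if drawn from them, are also biased (placebo mean off by about 10 to 20 mL in the two equal-dropout scenarios).
- **Drift plus such dropout leaving the arms unbalanced on baseline:** the treatment difference is biased too, by about 3-9 mL in mild to moderate scenarios and 12-21 mL when dropout is strongly arm-specific.
- **Constant slope:** no bias and no loss of precision was seen, whatever the dropout.

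The directions and conditions carry over to the trial; the mL values depend on the assumed SDs, slopes, dropout and 60 mL effect. For CAT only the algebra applies. Severity is low. FEV1 is an additional efficacy variable and CAT an outcomes-research measure; neither is in the testing sequence of section 4.2.4, and the MACE and exacerbation analyses do not use these models.

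**What to change.** Before unblinding:

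1. In the FEV1 MMRM (section 4.2.4.3), add baseline FEV1 by visit and, if the model converges, screening pre- and post-bronchodilator FEV1 by visit.
2. In the CAT MMRM (section 4.2.6.1), add baseline CAT by visit.
3. State the order of simplification if a fit fails: drop the screening-by-visit terms before giving up the unstructured covariance. The LABA and LABA/ICS subgroup analyses inherit the model and, being smaller, may need this rule most.

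The cost with eight FEV1 visits is 7 parameters for baseline by visit, or 3 × 7 = 21 with both screening terms. With ten CAT visits it is 9. That is little in a trial of 4,000 patients; the remaining price is a slightly higher risk of non-convergence.
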